9.2 SAMPLE SIZE DETERMINATION

Sample Size and Power. Our target sample size for the first trial is 14,442 patients, 4814 patients in each of the three study arms. The calculations below employ 80% power, overall Type I error rate of .05 with a Bonferroni correction for 3 pairwise comparisons of study arms (.05/3=.0167), and 2-sided hypothesis testing. Based on our prior analyses,^{26,27} we anticipate death or health plan disenrollment in 9.9% of sampled patients within 3 months of the intervention (receipt of the letter), with the remaining 90.1% contributing data in the 6-month interval of interest (days 91-270 post-intervention) – that is, we anticipate a per-arm sample size of $4814 \times .901 = 4337$.

For analyses of the primary outcome, absence of dispensing of targeted inappropriate prescription classes in days 91-270, we anticipate censoring in this interval for 13.5% of participants based on prior data. To make maximal use of observed data, we will use survival analysis to model time until an inappropriate prescription (a “failure”) in days 91-270. Detectable pairwise between-arm differences (e.g., between usual care and an intervention arm) are presented in Table 2 below for a range of possible percentages for “failure” = inappropriate prescribing of the targeted drug.

Table 2. Detectable pairwise between-arm differences in hazard of inappropriate prescription classes in days 91-270

Percent with inappropriate prescribing of targeted drug (“failure”), Study Arm 1	Detectable hazard ratio for inappropriate prescribing, Arm 2 versus Arm 1
40	.8860
50	.8979
60	.9067
70	.9136
75	.9165
80	.9192
85	.9216
90	.9239
95	.9260
99	.9267

For the range of “failure” percentages examined here, which reflect those seen in Martin et al,³ detectable hazard ratios range from 0.89 to 0.93. For example, if 75% of participants randomized to Arm 1 are observed to have a “failure” (prescription for a targeted inappropriate medication) by day 270, the detectable hazard ratio for an inappropriate prescription for Arm 2 versus Arm 1 is 0.9165, a

8.35% reduction in risk; the corresponding detectable “failure” probability for Arm 2 = 0.7193, a difference smaller – i.e., more precise – than that seen in Martin et al.³ Calculations for the secondary outcome of ≥50% reduction in dose are parallel.

For additional secondary outcomes, such as per-patient number of hospitalizations or ED visits, based upon prior data (mean of 0.35 hospitalizations per 6-month period and 0.4 ED visits per 6-month period), we will be able to detect rate ratios of 0.8856 and 0.8927, respectively (corresponding to intervention-related reductions of 11.4% and 10.7%), accounting for censoring due to death or disenrollment. For between-arm differences in mortality, assuming usual care 6-month mortality of 6.3% – likely an underestimate given a lag in ascertainment – and 7.6% censoring due to disenrollment based on information provided by the participating health plans, the detectable hazard ratio is 0.7356 corresponding to per-arm survival percentages of 93.7% versus 95.33% (absolute difference of 1.63%).

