9 STATISTICAL CONSIDERATIONS

9.1 STATISTICAL HYPOTHESES

Primary Endpoint:

We hypothesize that, compared to patients in the control group, patients who are in either intervention arm and receive information around inappropriate prescribing themselves along with their provider, or who have a provider that received the mailing, will have reduced inappropriate prescribing. Alternatively, our null hypothesis is that there will be no difference in the effects of the educational intervention at the end of the observation period.

Secondary Endpoint(s):

We hypothesize that education on inappropriate prescribing among patients/caregivers and their providers can reduce medication-related morbidity in patients with AD/ADRD and lead to an improvement

in medication safety for this vulnerable population. This will be measured by assessing evidence of dose reduction of the selected inappropriate medication, reduction in the prevalence of polypharmacy; reduction in the rates of emergency room visits; rates of hospitalizations; rates of non-acute institutional stays (e.g., skilled nursing facilities); overall health care utilization (number of outpatient visits, days hospitalized, emergency department visits, and non-acute institutional days); and in-hospital mortality.

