9.4 STATISTICAL ANALYSES

9.4.1 GENERAL APPROACH

In descriptive analyses, treatment arms will be compared regarding key patient characteristics, including age, gender, and renewal of inappropriate prescriptions in days 1-90, using percentages for categorical characteristics and means (standard deviations) or medians (interquartile range) for continuous characteristics, depending on the observed distributions. Analyses of study outcomes will employ two-sided hypothesis testing and an overall Type I error of 0.05, applying a Bonferroni correction to accommodate three pairwise comparisons of the three study arms. Covariates of *a priori* interest include patient age, gender, and renewal of inappropriate prescriptions in the blackout period. In addition, we will adjust for characteristics that are found to predict study outcomes, in order to increase precision for the comparison of study arms,²⁸ as well as for characteristics found to be related to censoring or other missing data, in order to reduce possible nonresponse bias.²⁹ All analyses will be intention-to-treat. Sex as a biological variable will be factored into all analyses.

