For the primary outcome (i.e., any post-intervention discontinuation of inappropriate prescribing during the 6-month period beginning 3 months after the mailing), as a first step, we will calculate crude arm-specific percentages, as well as Kaplan-Meier curves and log-rank testing. Covariate-adjusted comparisons of arms will be estimated using Cox proportional hazards modeling. Comparing active intervention arms to usual care, we hypothesize a hazard ratio of less than 1, indicating lower risk of an inappropriate prescription in days 91-270 in the active intervention arms. The index date for the survival analysis will be day 91. We chose the hazard ratio as method of aggregation as this allows the statistical analysis to account for censoring due to death or disenrollment. To account for mortality, anticipated to be approximately 6%, we also will conduct competing risk analyses³⁰ as well as cause-specific hazards modeling.³¹

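### Single-step Bonferroni across the three arms is valid, but Shaffer's step-down gives more power for the second and third comparisons at the same 5% family-wise error and the same N

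*Combined protocol and SAP*

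**What the plan says.** Section 9.2 sizes the first trial with an "overall Type I error rate of .05 with a Bonferroni correction for 3 pairwise comparisons of study arms (.05/3=.0167"), "2-sided hypothesis testing" and 80% power: "Our target sample size for the first trial is 14,442 patients, 4814 patients in each of the three study arms". Table 2 is built on that threshold.

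Section 9.4.1 carries the rule into the analysis of study outcomes, "applying a Bonferroni correction to accommodate three pairwise comparisons of the three study arms". No section gives a step-down, closed or ordered procedure, so the rule as written holds every pairwise test at .0167 whatever the other two show.

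The hypotheses concern more than one comparison. Section 9.1 says that "compared to patients in the control group, patients who are in either intervention arm" will have reduced inappropriate prescribing. Section 9.4.2 says: "Comparing active intervention arms to usual care, we hypothesize a hazard ratio of less than 1".

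**The concern.** The three null hypotheses are the three equalities among the same three arms (combined = usual care, provider-only = usual care, combined = provider-only). They are logically linked: if two hold, the third must hold. So if any one is false, at most one of the other two can be true. Single-step Bonferroni ignores this link and keeps guarding against two further false rejections when at most one is possible.

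What is at stake is power after the first rejection. The plan expects benefit in both intervention arms, so establishing one comparison answers only part of its question. The remaining comparisons also bear on a decision that the plan names: sections 1.1 and 4.1 say the provider-only arm may be dropped from the second trial in light of the first.

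**Working it through.** **Inputs from section 9.2.** 4814 patients per arm; 9.9% lost before day 91, leaving 4814 × 0.901 = 4337; 13.5% censored in days 91–270; 75% failure in the reference arm; detectable hazard ratio (HR) 0.9165; two-sided alpha 0.05/3 = 0.0167; 80% power.

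**Reproducing the plan's figure.**
- Failure probability in the second arm: 1 − 0.25^0.9165 = 0.7193, as stated.
- Expected events per pair: 4337 × 0.865 × (0.75 + 0.7193) = 5512.
- Events required (Schoenfeld): 4 × (2.3940 + 0.8416)² / (ln 0.9165)² = 5509 after rounding up.
- Power with 5512 events: 0.800. The worked example is right.

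**The two rules.**
- Bonferroni: all three p-values against .0167.
- Shaffer: the smallest p-value against .0167; if it is rejected, each of the other two against .05; otherwise stop.

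Shaffer's thresholds are never stricter than Bonferroni's, so it keeps every Bonferroni rejection. A single pairwise test of HR 0.9165 has power 0.800 at .0167 and 0.899 at .05.

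**Simulation.** At least 2,000,000 draws of three independent normal arm estimates, scaled so that HR 0.9165 between two arms gives a mean z of 2.3940 + 0.8416 = 3.2356. Holm's procedure, which does not use the logical link, is shown for comparison. Setting both intervention arms at HR 0.9165 against usual care is an assumption taken from the 75% row of Table 2.

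| Both arms at HR 0.9165 | Bonferroni | Holm | Shaffer |
|---|---|---|---|
| Each intervention arm vs usual care | 80.0% | 82.9% | 86.4% |
| Both shown | 68.7% | 74.4% | 81.5% |
| At least one rejection | 91.3% | 91.3% | 91.3% |

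**Range of assumed effects, same number of events.**

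| Both arms at | Both shown, Bonferroni | Both shown, Shaffer |
|---|---|---|
| HR 0.93 | 46% | 62% |
| HR 0.9165 | 69% | 81% |
| HR 0.90 | 89% | 95% |
| HR 0.88 | 98.2% | 99.4% |

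If only the combined arm works (HR 0.9165, provider-only at 1.0), its comparisons with usual care and with provider-only each go from 80% to 86%.

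**Family-wise error.** With all three arms equal it is 4.4% under either rule. With both intervention arms at HR 0.9165, so that only combined vs provider-only is truly null, it is 1.7% under Bonferroni and just under 5% under Shaffer. With a very large effect in one arm, Shaffer reaches 5.0%. The gap between 1.7% and 5% is the unused error that becomes power.

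**Equivalent sample size.** For Bonferroni to show both with probability 0.8147, two z-statistics with correlation 0.5 must both exceed 2.394, which needs a mean z of 3.612. The inflation is (3.612 / 3.2356)² = 1.246, and 14,442 × 1.246 is about 18,000 patients.

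**The case against.** Nothing in the plan is wrong, and Bonferroni is simple, familiar and consistently stated. Power is promised per pair, that promise is met, and the chance of a first rejection does not change. Showing both arms effective is not a declared power target, so the 18,000 figure only expresses the size of the gain; it is not a shortfall in the plan. HR 0.9165 is a detectable limit, not an expected effect, and the gain all but vanishes at HR 0.88 or stronger. These points stand, and they are why the change is optional.

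Three costs also stand:
- **Error on one contrast.** If both intervention arms work equally, the chance of falsely separating them rises from 1.7% to about 5%. That is within the plan's own 5%, but this contrast bears on whether provider-only is kept.
- **Intervals.** Bonferroni has matching 98.33% intervals; the step-down has no simple counterpart.
- **Scope and timing.** Section 9.4.1 applies the rule to study outcomes generally, so the change reaches the secondary outcomes too. The trial is open-label, and section 10.4 shows that patients had been randomized by July 2022. A looser second-step threshold is credible only if fixed before arms are compared. Section 9.4.6 plans no interim analysis, which helps, but the documents do not show whether that window is still open.

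One could also narrow the family to the two comparisons with usual care that section 9.1 states. Shaffer answers the three-comparison family that the plan actually wrote.

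None of this defeats the point: for that family, Shaffer rejects everything Bonferroni rejects, sometimes more, at the same family-wise error.

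**Conclusion.** The point holds as a low-cost improvement in efficiency; it is not an error. At the plan's own detectable effect in both intervention arms, power to show both is about 13 percentage points lower than it could be (69% against 81%), and power per comparison about 6 points lower (80% against 86%). Across assumed hazard ratios from 0.93 to 0.88 in both arms, the gain in showing both runs from 16 points down to about 1. The result rests on the stated event assumptions, on normally distributed log-hazard estimates, and on all three comparisons using the same population and model. Control is per outcome under either rule; neither adjusts across the secondary outcomes.

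**What to change.** Before arms are compared on outcomes, replace the Bonferroni rule in 9.4.1, and the matching wording in 9.2, with this: test the smallest of the three pairwise p-values against .0167; if it is rejected, test each of the other two against .05; otherwise stop. Add that all three tests for an outcome use the same population and model. Keep N, Table 2 and .0167 for sizing.

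Report 98.33% simultaneous intervals, and state that such an interval may include 1 for a comparison rejected at the second step. With both arms at HR 0.9165 this happens for an intervention-versus-usual-care comparison in about 13% of trials, and for any of the three in about 15%.

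The cost is a few sentences of wording, no added patients, and the interval and error trade-offs described above. If the sponsor prefers tests and intervals that always agree, it can keep Bonferroni and record that reason.

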9.3 POPULATIONS FOR ANALYSES

Intention-to-Treat (ITT) Analysis Population (all randomized participants):

All analyses will be intention to treat. We do not expect differential loss to follow up between the three arms of the study. For the time to event analysis patients will be censored from the analyses at the time of death, disenrollment from the health plan, loss of medical or pharmacy coverage, or change in eligibility for research based on health plan membership.

We will construct a detailed consort diagram showing the number of patients randomized to the three arms, the number of patients lost to follow up, excluded from analyses and the number of subjects included in the primary and secondary analysis. [See consort Draft. In section 1.2 (schema)]

[figure not shown]
9.4 STATISTICAL ANALYSES

9.4.1 GENERAL APPROACH

In descriptive analyses, treatment arms will be compared regarding key patient characteristics, including age, gender, and renewal of inappropriate prescriptions in days 1-90, using percentages for categorical characteristics and means (standard deviations) or medians (interquartile range) for continuous characteristics, depending on the observed distributions. Analyses of study outcomes will employ two-sided hypothesis testing and an overall Type I error of 0.05, applying a Bonferroni correction to accommodate three pairwise comparisons of the three study arms. Covariates of *a priori* interest include patient age, gender, and renewal of inappropriate prescriptions in the blackout period. In addition, we will adjust for characteristics that are found to predict study outcomes, in order to increase precision for the comparison of study arms,²⁸ as well as for characteristics found to be related to censoring or other missing data, in order to reduce possible nonresponse bias.²⁹ All analyses will be intention-to-treat. Sex as a biological variable will be factored into all analyses.

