1.	Diagnosis of AD/ADRD based on a modified list of the Chronic Conditions Data Warehouse codes, or treatment with a pharmacologic therapy used for AD (e.g., donepezil, rivastigmine, galantamine, or memantine) in the 365 days prior to or on cohort entry date. 
• The two AD/ADRD ICD-10 diagnosis codes must be ≥7 day apart and at least one of the codes is within 365 days of the cohort entry date.• Treatment is defined as use of an ADRD drug based on at least two dispensings in the 365 days prior to or cohort entry date.
2.	Evidence of prescribing within the past 3 months prior to or on the cohort entry date
3.	Age ≥50 years of age as of cohort entry date
4.	Continuous medical and pharmacy insurance coverage for at least the prior year.

Exclusion criteria:

1. Evidence of a recent institutional stay encounter in a skilled nursing facility, hospice, rehab center, nursing home, residential, and other non-hospital stays within the previous 90 days prior to or on cohort entry date..

2. Incomplete/missing prescriber ID or incomplete contact information for either patient or prescribing provider.
3. On “do not contact” list

Provider Inclusion Criteria:

1. Prescribing provider associated with most recent prescribing of a target drug

Feasibility analysis. We conducted a feasibility analysis using data from January 1, 2019 to January 31, 2021. During the study period, there were 99,826,441 unique members identified in the two health plans, of whom 66,862,829 were ineligible for research and excluded. After further excluding 32,832,930 members due to exclusion criteria (lacking pharmacy and medical coverage, < 50 years, or no diagnosis codes of ADRD drug or dispensing for ADRD), there were 130,682 members with AD/ADRD. We additionally excluded 104,423 patients without current evidence of inappropriate prescribing, resulting in a cohort of 26,259 trial-eligible patients. **The selection of participants for the feasibility analysis is shown in Figure 2. The flow diagram of participants is shown in Figure 3.**

Figure 2. Selection of participants for the feasibility analysis

[figure not shown]
[figure not shown]

Figure 3. Flow diagram of participants

Flow of Participants

1

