9.4.5 BASELINE DESCRIPTIVE STATISTICS

Demographics and baseline characteristics. Baseline and demographic characteristics will be based on claims data at the time of randomization. Frequency distribution and summary statistics will be presented by three intervention groups. Key demographics to be summarized include age in 5-year categories, sex, ethnicity, geographic region, Combined Comorbidity score, health care utilization indices and current use of inappropriate prescribing drugs. Categorical variables will be presented as frequencies and continuous variables as mean and SD. We will not use inferential statistics at baseline.

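### The primary analysis pre-specifies no pre-mailing measure of targeted-drug use, and so forgoes power that one baseline stratum or covariate could add at almost no cost

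*Combined protocol and SAP*

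**What the plan says.** - **Covariates.** Section 9.4.1 states that covariates of a priori "interest include patient age, gender, and renewal of inappropriate prescriptions in the blackout period". It then adds, without naming variables, a look-back window or a selection rule, that the models will also adjust for whatever turns out to predict outcomes (for precision) or to relate to censoring.
- **Primary analysis.** Section 9.4.2 begins with crude percentages, Kaplan-Meier curves and a log-rank test, and moves to covariate-adjusted Cox models. The Cox models adjust for any same-class dispensing in the blackout period and for its duration. The only stratification mentioned, as something that may be considered, is on blackout dispensing.
- **Entry.** Section 4.1 asks for "Evidence of prescribing within the past 3 months prior to or on the cohort entry date". It states no minimum number of targeted-drug fills, although the same list requires two dispensings where an AD drug is the qualifying criterion.
- **Data at hand.** Section 4.1 requires continuous medical and pharmacy coverage for at least the prior year. Section 9.4.3 derives mean daily dose over the six months before randomization for the dose-reduction outcome. Section 9.4.5 tabulates "health care utilization indices and current use of inappropriate prescribing drugs" at baseline, for description only.

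**The concern.** As the criteria read in Section 4.1, occasional and continuous users of the targeted drug can both enter. How much of the drug a patient was filling before the mailing should be among the better predictors of a fill in days 91-270. Section 9.4.2 itself calls blackout dispensing an important factor for the outcome, and the variable left out is its pre-randomization counterpart.

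Two things are at stake. First, when a strong prognostic variable is omitted from a log-rank or Cox analysis, the unadjusted hazard ratio lies nearer to 1 than the within-group ratio, and the test is less powerful than an adjusted one. Second, the drug-use variable that the plan does adjust for comes after randomization and may itself respond to the letter, so it is a poor substitute for baseline use.

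**Working it through.** **Step 1: the plan's own figure.** Inputs from Section 9.2:
- "The calculations below employ 80% power", "2-sided hypothesis testing" and "overall Type I error rate of .05 with a Bonferroni correction for 3 pairwise comparisons of study arms (.05/3=.0167";
- "Our target sample size for the first trial is 14,442 patients, 4814 patients in each of the three study arms", with the "remaining 90.1% contributing data in the 6-month interval of interest", so 4,814 × 0.901 = 4,337 per arm;
- 13.5% censored in days 91-270, 75% failure in Arm 1, detectable hazard ratio 0.9165.

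Arm 2 failure is 1 − 0.25^0.9165 = 0.7193, as stated. By Schoenfeld, the events needed are 4 × (2.394 + 0.842)² / (ln 0.9165)² ≈ 5,508. The events expected are 4,337 × 0.865 × (0.75 + 0.7193) ≈ 5,512. Power is 80.0%. No covariate enters, so the stated power is that of an unadjusted comparison.

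**Step 2: what adjustment would add.** The documents do not say how strongly prior use predicts refills, so the mixes below are assumptions. Each gives 75% failure overall in Arm 1. The simulation has 4,337 per arm, exponential times within groups, 13.5% of patients with uniform censoring and alpha 0.0167, with 1,000 to 1,500 runs per setting. Repeat runs differ by up to about 3 points. The result also depends on what is held fixed:
- *Reading 1:* 0.9165 is the hazard ratio within each use group.
- *Reading 2:* Arm 2 failure stays at the protocol's 0.7193.

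| Assumed mix (share of patients at failure %) | Reading 1: unadjusted / stratified | Reading 2: unadjusted / stratified |
|---|---|---|
| No heterogeneity | 82% / 82% | same setting |
| 30% at 65, 70% at 79.3 (weak) | 84% / 85% | not tabulated |
| 25% at 30, 75% at 90 | 62% / 87% | 93% / 99.5% |
| 40% at 52.5, 60% at 90 | 72% / 85% | 89% / 95.5% |
| 25/35/40% at 35/80/95.6 | 60% / 84% | 92% / 99.8% |

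The first row exceeds 80% because censored patients here contribute follow-up until censoring, whereas the plan's formula gives them no events.

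Under Reading 1 the unadjusted hazard ratios in the three strong mixes are 0.933, 0.926 and 0.935.

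**Step 3: why the readings differ.** In the 25/75 mix under Reading 1, Arm 2 failure is 0.25 × (1 − 0.7^0.9165) + 0.75 × (1 − 0.1^0.9165) = 0.25 × 0.2788 + 0.75 × 0.8788 = 0.7288. The arms then differ by 2.1 points, not the planned 75 − 71.93 = 3.07. The other two strong mixes give 0.7251 and 0.7286, or 2.5 and 2.1 points. Reading 1 therefore tests a smaller absolute effect than Section 9.2 does.

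**Step 4: a continuous baseline covariate as a cross-check.** With 0.9165 as the conditional ratio and a log-hazard SD of 0.25, 0.5, 0.75 or 1.0, unadjusted power is about 81%, 74%, 62% or 51%, against 84-85% adjusted. The standard error hardly moves (0.0258 to 0.0255); the change is in the hazard ratio (0.919 to 0.940 unadjusted). With 0.9165 as the marginal ratio, unadjusted power stays at about 84%, and adjustment raises it to about 92% (SD 0.5) or 99% (SD 1.0).

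**Step 5: blackout renewal as the substitute.** Assume SD 0.5 and that the letter also lowers renewal in days 1-90 by the same hazard ratio. Adjusting for renewal (yes/no) then gives a hazard ratio of 0.9315 and 64% power. No adjustment gives 0.9249 and 74%; adjusting for baseline use gives 0.916 and 84%.

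**The case against.** The strongest reply is that the plan already commits to adjusting for predictors of outcome, so if prior use is as prognostic as supposed it will be picked up. The covariate list is also not worded as exhaustive. This stands in part: a reader might infer that baseline use will never be adjusted for, and the documents do not support that. But the clause names no variable, window or rule, it chooses covariates from outcome data in an open-label trial, and it does not reach the log-rank test.

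A reader might also infer from the 60-72% figures that the trial is underpowered. That does not follow. Those figures hold 0.9165 within use groups, whereas Section 9.2 powers an unadjusted comparison of 75% with 71.93%. With that contrast kept, unadjusted power in the same mixes is about 89-93%.

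Nor is the unadjusted hazard ratio biased. The gap between it and the within-group ratio is non-collapsibility; the marginal ratio is a legitimate target and its null test is valid.

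Finally, that a single fill qualifies is a reading of Section 4.1, which refers to a manual of procedures for eligibility detail. The mixes are assumed, and a weak one makes the gain negligible.

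**Conclusion.** The point holds as a missed, nearly free improvement in the pre-specified analysis, not as an error in the sample size or a bias in the estimate. No pre-mailing measure of targeted-drug use is named for the primary analysis, the drug-use covariates that are named follow randomization, and the claims needed for a baseline measure are available.

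The gain ranges from 1 to 2 points of power if prior use is weakly prognostic to, in the strong mixes, roughly 13 to 25 points under Reading 1 (85 − 72 to 87 − 62) or about 6 to 8 points under Reading 2 (95.5 − 89 to 99.8 − 92). The range rests on assumed prognostic strength and on which hazard ratio 0.9165 is meant to be, which the plan does not say. The comparison of blackout adjustment with baseline adjustment is illustrative, because it assumes that the letter affects early renewal.

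**What to change.** In Sections 9.4.1 and 9.4.2:
1. Name one measure of targeted-class use before mailing, for example days supplied in the 180 days before mailing. Fix its definition and categories before any outcome data by arm are seen.
2. Use it as a stratum in the log-rank test and as a stratum or covariate in the primary Cox model, in preference to blackout-period dispensing and its duration.
3. State whether the conditional or the marginal hazard ratio is the target, and which of the two the 0.9165 in Section 9.2 represents.

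The cost is a few sentences of SAP text and one variable derived from claims already held. Sample size, eligibility and data collection do not change. The choice of measure and cut-points is for the trial team; what matters is that it is made in advance.
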